patient and clinician perception assessment scores. The baseline characterization for Phase 1 will provide patient background, history, and initial clinical evaluation. For Phase 2, baseline characterization will only include the initial clinical evaluation as no further initial evaluation is warranted. An acclimatization period is not necessary for Phase 2, as both devices will have been calibrated in Phase 1, requiring only a cannula change. Titration of therapy (Flow/FiO2) is only expected during Phase 1 (or in the event the patient decompensates and requires adjustment), as this study is a comparison of device efficacy. For the therapeutic characterization segment of each phase, final patient data for the corresponding device design will be recorded. Following this, the clinician and the patient will complete VAS perception scores corresponding to each device design. Primary and secondary outcomes will be evaluated and recorded upon the completion of all study phases. Tertiary outcomes will be evaluated and recorded upon the completion of each study phase.

This study will be conducted in an inpatient or outpatient hospital setting where patient testing can be performed with appropriate medical supervision and staff training to maintain patient safety. All respiratory interventions will be tracked within the study window for each patient.

V. Subject Enrollment

Subjects will be recruited by investigators using patient medical records and initial patient contact. Subjects will be consented prior to participation in this study (Aims 1-3). Once consented, the participants and investigators will complete data collection in all Aims during the trial period. Subjects have the right to withdraw consent to participate in this study at any time, for any reason.

Sample Size:

To provide a sufficiently powered sample dataset, we will enroll up to 32 subjects to complete this study on designs, with a calculated sample size of N=26 plus a 20% failure/fallout rate. This will provide sufficient data to adequately inform on the study objectives.

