This sample size was estimated through use of references that (1) approximated minimal clinical important difference of dyspnea (modified Borg scale) and (2) approximated expected standard deviation of prior datasets measuring dyspnea.¹⁶⁻¹⁸ Estimated minimal clinical important difference of dyspnea was determined to be a difference value of 2 in modified Borg for dyspnea.¹⁶ In reviewing publications from Roca 2010 and Schwabbauer 2014, it was estimated that a value of 2 to 3 was suitable for the standard deviation of dyspnea for the modified Borg scale. Therefore, for this study, using the paired t-test sample size calculation, with an expected difference of 2, and an expected standard deviation of 3, using a desired power of 90% with alpha=0.05, the sample size is estimated at 26 to show if the data may or may not have any difference.

Vapotherm, Inc

New HVNI Device Design Efficacy in Relieving Dyspnea

Confidential

VI. Study Procedures

This validation study is non-blinded to investigators and patients by necessity, as there is a distinct difference in size and appearance between the Precision Flow and HVT2.0 HVNI device designs. However, patients may not know the difference between conventional and new device design. This study is a crossover design trial that will measure, ventilation, comfort, and efficacy—specifically the effect of relief of dyspnea as demonstrated by RPD assessment and measured by TcPCO₂ device. In addition, patient physiologic outcomes (e.g. HR, RR, BP, SpO₂), as well as patient & clinician assessment scores will be evaluated and recorded. Figure 1 illustrates a flowchart of overall study procedures.

Screening, Enrollment, & Management

During screening, subjects will be asked to participate in this study, and if so, they will provide informed consent prior to enrollment. Subjects will be instructed that if at any time during the study that they wish to discontinue the study, they are free to stop the testing and discontinue study participation at any time. All study procedures will be explained to the subject prior to starting any procedures, and all participants will be given a copy of the informed consent form.

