Upon enrollment, appropriate study data will be collected (see below under Data Collection), including patient demographics (e.g. age, gender, ethnicity, race), anthropometrics (e.g. weight, height, BMI, and applicable medical history) including a detailed focus on the patient's current respiratory status (LTOT user, positive-airway pressure therapy [NIPPV] user, current respiratory therapy). Subjects will be managed by routine care while study data is captured as shown in the timeline below (Table 1). All decision making with regard to patient participation will be made in conjunction with appropriate medical professionals per standard practice at the trial site. Time required from screening to the end of the study, is estimated to be 1.65 hours in duration.

[figure not shown]

Figure 1. Framework of the clinical study procedures discussed within this protocol. Each Phase is designated by a Precision Flow or HVT2.0 design.

Vapotherm, Inc

New HVNI Device Design Efficacy in Relieving Dyspnea

Confidential

Phase 1 – Precision Flow (Control) or HVT2.0 (Test) design (order randomized)

This test session is represented by Phase 1 in Figure 1, where the patient is placed on HVNI device therapy with the order-randomized conventional or new device design. Phase 1 will follow four distinct segments: (1) baseline characterization, (2) therapy acclimatization, (3) therapeutic characterization, (4) patient and clinician assessment scores.

Baseline Characterization will be performed just prior to the therapy acclimatization segment of this Phase. If, for any reason, the clinician does not deem the patient appropriate for the study, per inclusion/exclusion criteria, they may stop procedures during baseline characterization. The patient may be sitting or lying down in a comfortable environment. The patient will be set up for study testing with appropriate data recording devices. While subject is at rest, the following data will be collected (see Table 1): RR, HR, BP, SpO₂, TcPCO₂ and RPD (Modified Borg scale 0-10). For the RPD, the clinician will record patient scores. The patient may or may not be on HVNI therapy at this the time the RPD is completed. The Phase 1, baseline characterization will include recording data while the patient is in an uncompromised state (e.g. ON current oxygen therapy, if applicable).

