Baseline Characterization will be performed just prior to the therapy acclimatization segment of this Phase. If, for any reason, the clinician does not deem the patient appropriate for the study, per inclusion/exclusion criteria, they may stop procedures during baseline characterization. Sitting down in a comfortable environment, the patient will be setup and prepared for the testing with appropriate data recording devices. The patient will be ON current/home oxygen therapy at this time (if applicable). While the subject is at rest, the following data will be collected (see Table 1): RR, HR, BP, SpO₂, tcPCO₂ and RPD (Modified Borg scale 0-10). For the RPD, the clinician will record patient scores.

Therapeutic Characterization will be performed immediately after the baseline segment is completed in Phase 2 only. Once the respiratory therapist or other clinician skilled in management of HVNI deems that the HVNI settings are having a therapeutic effect, the following data will be collected (see Table 1): RR, HR, BP, SpO₂, TcPCO₂ and RPD (Modified Borg scale 0-10). For the RPD, the clinician will record patient scores.

Patient & Clinician Perception Assessments will be performed by the clinician or therapist performing this phase's testing procedures. Immediately following the completion of this phase, the continuous Visual Analogue Scale (VAS) will be completed for each of the five endpoints for clinician assessment and the two endpoints for patient assessment. For patient perception these endpoints include: (1) relief of symptoms, and (2) comfort/tolerance. For clinician perception these endpoints include: (1) technical/clinical difficulties, (2) patient comfort & tolerance, (3) ease of use, (4) monitoring & support for therapy, and (5) expected/perceived patient outcomes.

Vapotherm, Inc
New HVNI Device Design Efficacy in Relieving Dyspnea
Confidential

Upon completion of Phase 2, the study testing procedures will be deemed completed, and any final study data will be recorded at this time. At this time, the patient may resume current/home oxygen therapy.

Other Medical Care

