- Clinician perception of Monitoring and support of therapy required (adjustments, refilling fluids, adjusting interface), ranging from Minimal to Frequent, as continuous VAS.

VIII. Statistical Analysis

Baseline patient demographics and characteristics will be summarized, compared, and appropriate statistical testing will be performed for the continuous and categorical variables. Assuming a non-normal data distribution for this crossover order-randomized study design, the non-parametric Wilcoxon Signed Rank Sum test will be performed with significance interval of 0.05 on all applicable variables. Parametric analytical analogues (e.g. t-test) will be use if the measurements present a normal distribution. Otherwise, for the categorical variables, the Fisher's Exact test will be performed. Data will be compared and graphed accordingly for a visual comparison with accompanied statistical notations.

IX. Risks and Discomforts

This validation study does not present significant risk to patients, as supplemental oxygen is routinely provided to patients as a standard practice in hospitals¹⁹. Use of high flow nasal cannula (HFNC) therapy has no known risks and has been used in clinical settings for approximately 17 years. Additionally, there are no known reports of adverse events related to the administration of high nasal flows when the gas has been appropriately conditioned to near body temperature and fully humidified. Existing literature indicates that approximately only 4 cmH₂O of distending pressure may be generated in the upper airway, which is well below any known threshold for injury.^{20,21} Furthermore, it has been demonstrated that delivery of high flows of conditioned gas from a nasal cannula has a positive effect on airway mucosal function.^{22,23} The patients enrolled in this study will be closely monitored as part of standard medical practice.

For these reasons, we have determined that this study represents non-significant risk to the subjects. The high flow nasal cannula system used has no known risk and has been used in hospitals for approximately 17 years. During both study phases, patients will be closely monitored as part of the normal care. Patients may experience mild discomfort from a cannula in contact with their nose, face or around their ears and possibly a runny nose from the humidity contained in the gas flow.

X. Potential Benefits

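### Section VIII specifies a plain paired test that uses neither the randomised device order nor the phase-baseline readings, and it names no interval for the device difference

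*Combined protocol and SAP*

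**What the plan says.** - **Design.** Section IV describes a crossover with randomised device order, completed in one session. Titration is expected in Phase 1 only, and Phase 2 has no acclimatization.
- **Baselines.** RPD, TcPCO2, SpO2 and vital signs are recorded before therapy in both phases. For Phase 1, Section VI says "While subject is at rest, the following data will be collected (see Table 1"). Its Phase 2 text lists the same measurements and adds "The patient will be ON current/home oxygen therapy at this time (if applicable"). Section VII has RPD and TcCO2 recorded in every segment of every phase.
- **Endpoint.** Section II makes relief of dyspnea on the modified Borg scale primary. It does not say whether that means the on-therapy score or a change from baseline.
- **Analysis.** Section VIII assumes non-normal data and makes the Wilcoxon signed rank test the default at the 0.05 level. The alternative is: "Parametric analytical analogues (e.g. t-test) will be use if the measurements present a normal distribution". No order or period term, baseline covariate, change score or confidence interval is named.
- **Sample size.** Section V uses a paired t-test "with an expected difference of 2, and an expected standard deviation of 3", "using a desired power of 90% with alpha=0.05", and concludes that "the sample size is estimated at 26 to show if the data may or may not have any difference".

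**The concern.** The two phases are not run alike. In Phase 1 the therapeutic reading follows 5 to 10 minutes of acclimatization and a further 5 to 10 minutes. In Phase 2 it follows the baseline directly, once the clinician judges the settings effective. A systematic shift between Phase 1 and Phase 2 scores is therefore plausible. With balanced orders such a shift does not bias a paired comparison, but the plain test counts it as random error.

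The phase baselines may also carry information about within-patient change during the session, and Section VIII gives them no stated role. The sponsor wants to show that the devices perform alike, so the argument rests on how precisely the device difference is estimated. A p-value from a plain paired test does not report that precision. Leaving the role of the baselines open also lets the form of the primary variable be chosen after the data are seen.

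**Working it through.** **Inputs.** From Section V: n=26, difference 2, SD 3, power 90%, alpha 0.05 (taken as two-sided). SD 3 is treated as the SD of the paired difference, as the plan's own calculation implies. Not in the documents, so assumed: r (the correlation between the baseline difference and the outcome difference), the size of any period effect, and the amount of carry-over.

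**1. The plan's figure.** A noncentral-t paired calculation gives power 0.904 at n=26 and 0.892 at n=25, so 26 reproduces.

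**2. Unadjusted precision.** Half-width = t(25) × SD/√n = 2.0595 × 3/√26 = 1.21.

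**3. Order term.** Suppose a period effect moves the within-patient device difference by +1 in one order and −1 in the other, with 13 patients per order.
- Without the term, the expected variance is 9 + 26/25 = 10.04, so SD 3.17 and half-width 2.0595 × 3.17/√26 = 1.28.
- With the term, it is t(24) × 3/√26 = 2.0639 × 3/√26 = 1.21.
- Simulated average half-widths are 1.26 and 1.20. They run slightly lower because a sample SD averages a little below the true SD.
- With no period effect the term costs almost nothing: 1.214 against 1.212.

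**4. Baseline difference as covariate.** Half-width = t(24) × 3 × √[(1−r²) × 24/(23 × 26)].

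| r | half-width | against 1.21 |
|---|---|---|
| 0 | 1.24 | +2.4% |
| 0.2 | 1.22 | +0.3% |
| 0.3 | 1.18 | −2.3% |
| 0.5 | 1.07 | −11.3% |
| 0.7 | 0.89 | −26.9% |

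Break-even is r≈0.21 at n=26 and 0.19 at n=32. These figures are for the covariate alone. With order also in the model (23 degrees of freedom), the simulated average at r=0 is 1.23, against 1.20 unadjusted. With SD 2, every half-width is multiplied by 2/3 and the percentages do not change.

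**5. Simple change scores.** With equal baseline and outcome SDs, half-width = 2.0595 × 3 × √[2(1−r)/26]. That is 1.43 at r=0.3 (18% wider than unadjusted), equal to unadjusted at r=0.5, and narrower only above that.

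**6. Carry-over into the Phase 2 baseline only.** Let a fraction c of the Phase 1 relief persist into that baseline, let the true device difference be δ, and let baseline and outcome differences have equal SDs.
- The mean baseline difference then shifts by −cδ/2, so the adjusted estimate becomes δ + r × cδ/2.
- With δ=2 and r=0.5: 2 + 0.5 × 0.5 = 2.25 at c=0.5, and 2 + 0.5 × 1 = 2.50 at c=1. Simulation with order in the model agrees (2.25 and 2.50), against 2.0 unadjusted.
- With δ=0 there is no bias.

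**The case against.** A reader might infer that each baseline is an off-device reading, that the plan throws these readings away, and that adjusting for them would narrow the interval at no cost. The documents support none of this.

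- **Off-device is not assured.** The Phase 1 baseline may be taken while the patient is on HVNI, and Section VI allows patients who were already on it before the study. The Phase 2 baseline is on current or home oxygen only where that applies. Section IV describes the changeover as no more than a change of cannula, and no washout is stated. If the patient stays on HVNI, the Phase 2 baseline may largely repeat the Phase 1 outcome. Posture also differs: sitting or lying in Phase 1, sitting in Phase 2.
- **Discarding is not stated.** The plan is silent. An endpoint called relief leaves change from baseline neither specified nor excluded.
- **The gain is not guaranteed.** The documents give no r. The 1.65 hours in Section VI runs from screening to study end. The timed steps between the two baselines total 10 to 20 minutes, plus untimed ones, so the baseline difference may be mostly rating noise and r may be low. At r=0.3 the gain is only 0.03 Borg units.
- **There is a cost.** Order and baseline together use two degrees of freedom, and the bias in step 6 is not trivial.
- **The default test is non-parametric.** A linear model for a 0–10 score departs from the plan's Wilcoxon default, and the interval discussed here is one the plan does not call for.

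All of this stands against making the baseline-adjusted model primary now. It does not touch the order term or the reported interval. Nor is the unadjusted estimate safe in every case. In a simulation where half of the baseline residue also reached the Phase 2 outcome, a true difference of 2 averaged 1.73 or 1.51 unadjusted (half or all of the Phase 1 relief persisting into the baseline), against 1.98 and 2.00 adjusted. That is a reason to show both.

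**Conclusion.** The point holds in two parts of different strength.

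**Order term and interval: firm.** Order is randomised, the phases differ in procedure, and Section VIII uses neither fact. With an assumed period effect of 1 Borg unit, the plain test's average half-width is about 1.26 against 1.20 with the term. If there is no period effect, almost nothing is lost.

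**Baseline adjustment: conditional.** It helps if r exceeds about 0.2 (from 1.21 to 1.07 at r=0.5) and costs at most about 2.4% in width when there is no carry-over. When the devices differ and Phase 1 relief persists into the Phase 2 baseline, it can overstate the difference: 2 becomes 2.25 to 2.50 at r=0.5. It merits a pre-specified analysis beside the estimate without baseline adjustment, not the primary place while the state of the patient at each baseline is unclear.

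These sizes rest on SD 3 for the paired difference, balanced orders, and assumed values of r, period effect and carry-over.

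**What to change.** In Section VIII, before any comparison of the devices:

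1. Define the primary variable as the within-patient difference in RPD at therapeutic characterization, HVT2.0 minus Precision Flow.
2. Make the primary analysis a linear model of that difference with device order, coded +1/−1 so that the intercept is the device difference. Report it with its 95% CI.
3. Pre-specify the same model with the difference in phase-baseline RPD added, evaluated at zero baseline difference. Report it beside the estimate without baseline adjustment.
4. Do not analyse simple change scores. Keep the Wilcoxon signed rank test as a sensitivity analysis.
5. Use the same form for TcPCO2 and the vital signs.
6. Reconcile Sections IV and VI on the therapy in use at each baseline and on the changeover between devices. Until that is done, the baseline-adjusted model should not become primary.

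The analysis changes need SAP wording and no new data. They cost one degree of freedom for order and a second in the baseline-adjusted model, plus the carry-over risk described above, which is why both estimates are shown.
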